6.2.4.1.2. MAR Multiple Imputation

All missing data will be imputed using the predictive mean matching multiple imputation method (Heitjan and Little 1991, Schenker and Taylor 1996) under MAR data assumption using fully conditional specification (FCS) method. The imputation model will include age group at baseline, region, treatment arm, MD-CRS part II total score at baseline, week 9 and week 12.

The imputation under the MAR assumption corresponds to a full treatment effect observed in the mITT population. Therefore, the results from the tipping point analysis with $\delta = 0$ will be used for this sensitivity analysis; see Section 6.2.4.1.1 for details.

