2.4. Sample Size and Power Considerations

The initial sample size estimation of approximately 185 patients randomized to TEV-50717 versus placebo in a 2:1 ratio (approximately 124 in the TEV-50717 group; approximately 61 in the placebo group) is the sample size required to obtain a statistically significant result in the primary analysis based on a 1-sided test for mean difference at a significance level of $\alpha=0.025$ with a power of approximately 90%, assuming a mean difference of 1.8 and a standard deviation (SD) of 3.5 in each treatment group.

Based on Protocol Amendment 05, the initial planned sample size has been reduced to approximately 65 patients randomized to TEV-50717 versus placebo in a 2:1 ratio (approximately 43 in the TEV-50717 group; approximately 22 in the placebo group).

The initial assumptions regarding the mean difference and SD are based on the change from baseline to month 6 in patients treated with trihexyphenidyl reported by [Battini et al \(2014\)](#), assuming an effect size of 55% for TEV-50717 versus placebo. The effect size of 55% was assumed based on the observed effect sizes of TEV-50717 in the pivotal studies in Huntington's disease and tardive dyskinesia. In the current study, these assumptions correspond to a mean difference of 2.0 in MD-CRS part II total score and an SD of 3.5 in each treatment group.

The rate of missing not at random (MNAR) data for the primary analysis is expected to be 10%. MNAR data will be imputed in a conservative manner as if they were obtained from patients in the placebo treatment group, regardless of the actual treatment group. As a result, the mean difference is expected to be reduced from 2.0 to 1.8 in the primary analysis. The impact of the missing data imputation on the SD is negligible.

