6.2.3. Primary Efficacy Analysis

The primary analysis will be a mixed-model repeated-measures (MMRM) with the change in MD-CRS part II total score as the dependent variable. The model will include fixed effects for treatment group, week (as a categorical variable with 3 levels: weeks 9, 12, and 15), and treatment group by week interaction. The baseline MD-CRS part II total score, age group at baseline (2 levels: 6 to <12 years; 12 through 18 years, inclusive), and region (US; non-US) will be included as covariates. The unstructured covariance matrix will be used in the model. In cases where the model does not converge, the Maximum-Likelihood estimation method will be used instead of the default Restricted Maximum-Likelihood. If the model still does not converge, then a simpler covariance structure with fewer parameters will be used, according to the following order: Heterogeneous Autoregressive (1), Heterogeneous Compound Symmetry, Autoregressive (1), and Compound Symmetry. The Kenward-Roger approximation will be used to estimate denominator degrees of freedom.

Missing data will be classified as MAR and MNAR, as described in Section 4.3. MNAR data will be imputed using the jump-to-reference method, and MAR data will be imputed based on the randomized treatment group. The details are described below:

1. Missing data will be imputed in 2 separate subgroups. The MAR subgroup will contain all patients randomized to a TEV-50717 treatment group without missing data at week 15 or have a MAR missing data mechanism. The MNAR subgroup will contain all patients randomized to placebo as well as patients randomized to receive TEV-50717 with missing data at week 15 with an MNAR missing data mechanism.
2. Data will be imputed for patients with missing data at week 15 using a predictive mean matching multiple imputation method. Multiple imputations will be performed within each subgroup:
 - a. Under a MNAR data assumption, patients in the MNAR subgroup will have their missing data at week 15 imputed as if they behaved like placebo treated patients after dropping out. Only placebo patients with complete data will be included in the imputation model.
 - b. All other patients will have data imputed from a model derived from their assigned treatment group (imputation under MAR assumption).

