6.2.4.1. Sensitivity Analyses for Assumptions of Missing Data Mechanism

Sensitivity analyses for assumptions of missing data mechanism include the MNAR tipping point analysis and the MAR multiple imputations.

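### The MAR sensitivity analysis (SAP 6.2.4.1.2) changes the imputation model as well as the missing-data assumption, so it does not isolate the effect of jump-to-reference

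*SAP*

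**What the plan says.** **Primary analysis (SAP 6.2.3, Appendix 1).** TEV-50717 patients who are complete at week 15 or classed MAR form one subgroup. Placebo patients and TEV-50717 patients classed MNAR form the other. "Multiple imputations will be performed within each subgroup", and outside the MNAR cases "All other patients will have data imputed from a model derived from their assigned treatment group (imputation under MAR assumption"). Appendix 1 codes this as separate PROC MI calls per subgroup, for week 9, then 12, then 15, with monotone predictive mean matching.

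**MAR check (SAP 6.2.4.1.2, Appendix 2).** The method is fully conditional specification (FCS) with predictive mean matching. "The imputation model will include age group at baseline, region, treatment arm, MD-CRS part II total score at baseline, week 9 and week 12". The result is read from the tipping-point run at shift 0. Appendix 2 is a single PROC MI call on both arms, with arm in the variable list, no subsetting by arm and no interaction with arm.

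**Where the check is filed (SAP 6.2.4.1).** "Sensitivity analyses for assumptions of missing data mechanism include the MNAR tipping point analysis and the MAR multiple imputations". Checks of the statistical model have their own section, 6.2.4.2.

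**Expected cost of the MNAR assumption (SAP 2.4).** With 10% MNAR data, the mean difference is expected to fall from 2.0 to 1.8.

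**The concern.** A check of the missing-data mechanism is most useful when only the mechanism changes. Here the imputation model changes too. In the primary, the regression slopes and the matching donors for a MAR patient come from that patient's own arm. In the check, slopes are common to both arms and a donor may come from the other arm. Placebo patients, and TEV-50717 patients already classed MAR, are therefore imputed differently although nothing about their assumption has changed.

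What is at stake is attribution. If the MAR estimate differs from the primary, the reader cannot tell how much is the jump-to-reference penalty and how much is the change of model. If the two agree, the components may have offset each other.

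**Working it through.** **1. The plan's own figures.** Inputs from SAP 2.4: "approximately 185 patients randomized to TEV-50717 versus placebo in a 2:1 ratio", "assuming a mean difference of 1.8 and a standard deviation (SD) of 3.5 in each treatment group", one-sided alpha 0.025, power about 90%.
- Placebo patients needed at 2:1: (1.960 + 1.282)² × 3.5² × (1 + 1/2) / 1.8² = 59.6, so 60, and 180 in total. This is within 3% of the stated 185. Power at 124/61 is 0.908.
- Dilution by jump-to-reference: 2.0 × (1 − 0.10) = 1.8, as stated. The plan's expected mechanism effect is 0.2 points.

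**2. A logical test.** Suppose blinded review classed every dropout as MAR (for example lost to follow-up or COVID-19, SAP 4.3). The primary would then already be a MAR analysis, and a check of the mechanism alone should reproduce it up to Monte Carlo error. Under this plan the two would still differ, because one uses subgroup models and the other a pooled model.

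**3. Size at the reduced sample** ("approximately 43 in the TEV-50717 group; approximately 22 in the placebo group"; SD 3.5, true difference 2.0). Three analyses of the same simulated data were compared:
- A: subgroup-sequential imputation with jump-to-reference (the primary).
- B: the same imputation with all missing data treated as MAR.
- C: pooled FCS imputation with an arm main effect, under MAR (the planned check).

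A to B is the mechanism alone; B to C is the model switch alone. Assumptions not in the SAP: compound-symmetric visit correlation, dropout in both arms after week 9, all TEV-50717 dropouts MNAR in A, 5 donors, and a week-15 ANCOVA in place of the MMRM. Signed values are mean shifts towards a smaller drug effect.

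| Correlation | Dropout | Mechanism, mean absolute | Switch, mean absolute | Mechanism, signed | Switch, signed |
|---|---|---|---|---|---|
| 0.5 | 10% | 0.154 | 0.063 | 0.140 | 0.021 |
| 0.7 | 10% | 0.132 | 0.062 | 0.127 | 0.035 |
| 0.7 | 20% | 0.253 | 0.110 | 0.216 | 0.059 |
| 0.6 | 10% | 0.16 | 0.08 | 0.14 | 0.03 |
| 0.6 | 20% | 0.30 | 0.15 | 0.28 | 0.08 |

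The first three rows use 60 trials with 200 imputations each. Their Monte Carlo noise (B run twice) is 0.016 to 0.030. In B to C the signed shift runs opposite to B to A only in label: both A and C show a smaller drug effect than B.

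Further runs of the switch alone (90 trials, 200 imputations) gave, as absolute and signed shifts, 0.07 and 0.04 (correlation 0.6, 10% dropout), 0.11 and 0.07 (0.6, 15%), and 0.10 and 0.07 (0.8, 15%).

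Runs with only 40 imputations (200 trials), some with a different correlation in placebo, gave absolute switches of 0.087 to 0.152 and signed switches of 0.024 to 0.098. Their absolute values carry more Monte Carlo noise.

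**4. Ratios of switch to mechanism, from the table.**
- Absolute: 0.063/0.154 = 41%, 0.062/0.132 = 47%, 0.110/0.253 = 43%, 0.08/0.16 = 50%, 0.15/0.30 = 50%.
- Signed: 0.021/0.140 = 15%, 0.035/0.127 = 28%, 0.059/0.216 = 27%, 0.03/0.14 = 21%, 0.08/0.28 = 29%.

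**5. Against sampling error.** The unadjusted standard error is 3.5 × √(1/43 + 1/22) = 0.92; the simulations gave about 0.96. An absolute shift of 0.06 to 0.15 is 6% to 16% of 0.96. A signed shift of 0.03 to 0.08 is 3% to 8%.

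**The case against.** The SAP states the aim of 6.2.4 only as robustness of the primary analysis, and 6.2.4.1.2 promises no more than imputation of all missing data under MAR. The shift-0 run does that, and it is the natural anchor for the tipping-point grid. The grid itself varies the assumption with the imputation model held fixed. The week-15 ANCOVA without imputation (6.2.4.3) can be set beside the ANCOVA after jump-to-reference (6.2.4.2.1). The analysis is supportive, has no multiplicity control (Section 7), and on average slightly understates the drug effect rather than flattering it. All of this stands.

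It does not supply the missing comparison. The grid applies its shift to all TEV-50717 dropouts whatever their reason, and no grid point corresponds to the jump-to-reference primary. The ANCOVA without imputation drops patients with no week-15 value, so it too changes more than the assumption. The SAP also follows the one-change principle elsewhere: the ANCOVA check in 6.2.4.2.1 keeps the primary imputation and replaces only the analysis step.

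Stronger inferences are not supported:
- A reader might infer that the MAR check is invalid. It is not.
- A reader might count sequential versus FCS as a separate third change. With monotone dropout the two should largely agree; pooling the arms is the main difference.
- A reader might set the absolute shift against the 0.2 points of Section 2.4 and call it a third to a half of the signal. That divides a mean absolute deviation by an expected signed change. At 15% dropout, all MNAR, the matching dilution would also be 2.0 × 0.15 = 0.3 rather than 0.2.

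**Conclusion.** The point holds, at minor severity. The primary and the planned MAR check differ in two respects, the assumption for MNAR patients and the imputation model, so their difference does not measure the jump-to-reference assumption alone. Across the assumed settings (correlation 0.5 to 0.8, dropout 10% to 20%, 5 donors), the model switch is worth about 0.06 to 0.15 points in absolute terms. Signed, most scenarios lie between 0.03 and 0.08 points towards a smaller drug effect, with extremes of 0.02 and 0.10 over all runs. In the tabulated scenarios this is roughly 40% to 50% (absolute) or 20% to 30% (signed, lowest 15%) of the mechanism effect. It is small beside the standard error, does not touch the primary test, and would seldom change the trial's conclusion. The sizes rest on the simulation assumptions; the confounding itself follows from the text and the two appendices.

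**What to change.** In 6.2.4.1.2, replace the reuse of the shift-0 result with a sentence to this effect: *the imputation of Section 6.2.3 and Appendix 1 is repeated with all missing TEV-50717 data classified as MAR, all other steps unchanged.* Keep the shift-0 run as the starting point of the tipping-point grid. Carry the change to the key secondary endpoints in 6.3.1.2, using the extended visit sequence that 6.3.1.1 sets for CaGI-I and CGI-I.

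The cost is one sentence and one more run of existing code per endpoint with the missing-data flag set to MAR; no new data are needed. The one drawback is that the MAR estimate will differ slightly from the start of the tipping-point grid, which a table footnote can explain.

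Two separate slips in the printed code should be corrected before any comparison is made. The week-15 reference-group call in Appendix 1 uses a different variable name and code value for the MNAR flag than the earlier calls. Appendix 2 Step 2 outputs weeks 9, 8 and 12, so it gives no week-15 estimate.

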6.2.4.2. Sensitivity Analysis for the Statistical Model

Sensitivity analyses for the statistical model include the analysis of covariance (ANCOVA) and the primary model rerun with a reduced number of covariates.

6.2.4.2.1. Analysis of Covariance

The ANCOVA model will be used for week 15 MD-CRS part II total score change from baseline data following imputation using the same approach as described in Section 6.2.3, steps 1-2. The ANCOVA model will replace the MMRM analysis in step 3 of Section 6.2.3 and will include age group at baseline, region, baseline MD-CRS part II total score, and treatment as covariates. The SAS code for this model is as follows:

```
proc mixed;  
  class arm agegrp region;  
  model chg=arm agegrp region base;  
  lsmeans arm / diff cl;  
where avisitn=15;  
run;
```

6.2.4.2.2. Primary Analysis With Reduced Number of Covariates

Primary analysis, including only the following covariates: treatment group, week, and treatment group by week interaction will be run as described in Section 6.2.3. The MAR/MNAR multiple imputation models will include only these limited covariates. After obtaining complete data sets for MAR/MNAR subgroups, they will be combined and the complete data set will be used in the analysis with the same covariates.

6.2.4.3. Other Sensitivity Analyses

Other sensitivity analyses will include the primary model repeated on the different subsets of patients and at the different time points.

The primary model as described in Section 6.2.3 will be repeated using

- ITT analysis set;
- mITTA analysis set;
- mITTB analysis set;
- PP analysis set.

ANCOVA model, as described in Section 6.2.4.2.1, but without the multiple imputation, will be applied for MD-CRS part II total score change from baseline to

- week 9;
- week 12;
- week 15.

6.2.5. Retrospective Power and Sample Size

The following analyses will be performed to quantify the impact of the reduction in sample size on the power, based on the actual final data:

- Conditional power for $n=185$ (the initially planned minimal sample size), based on the observed effect size at the end of the study
- Sample size required to power the study (90%) at $\alpha=0.025$, based on the observed effect size at the end of the study
- Effect size and difference in change in MD-CRS II based on the observed SD needed in order to be powered (90%) for the given final sample size

The retrospective analyses will be conducted using the definitions and methods that were used in the interim analysis, see Section 10.4 and 10.5.

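### The first two calculations in SAP Section 6.2.5 re-express the final p-value and do not measure the power lost by cutting the sample from 185 to 65

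*SAP*

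**What the plan says.** Section 2.4 justifies the initial sample of about 185, randomised 2:1 ("approximately 124 in the TEV-50717 group; approximately 61 in the placebo group"), at 1-sided alpha 0.025 "with a power of approximately 90%, assuming a mean difference of 1.8 and a standard deviation (SD) of 3.5 in each treatment group". The 1.8 already carries a penalty for data missing not at random: "the mean difference is expected to be reduced from 2.0 to 1.8 in the primary analysis". The section then records the reduction to about 65 patients (about 43 and 22) and gives no power for that number.

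Section 6.2.5 plans three calculations "to quantify the impact of the reduction in sample size on the power, based on the actual final data":

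1. conditional power for n=185, "based on the observed effect size at the end of the study";
2. the sample size that would give 90% power, also at the observed effect;
3. the effect size and difference that would have 90% power at the final sample size, using the observed SD.

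The methods are taken from Sections 10.4 and 10.5. Section 10.4 sets the true effect equal to the interim point estimate and says that the initial planning assumptions are not used. Section 10.5 only converts an mITT count into a randomised count.

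**The concern.** The power lost by reducing a sample is a property of the design. It compares the chance of success at 185 and at 65 under one fixed assumed effect. Items 1 and 2 make no such comparison. They replace the assumed effect with the estimate from the 65 patients, and the method they borrow sets the planning assumptions aside.

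Item 1 also uses the data twice: as evidence already accrued, and as the assumed truth for about 120 further patients who will not be enrolled. At an interim look that can inform whether to continue. At the end of the trial there is no such decision.

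At stake is how a near miss is read. Section 6.2.5 places no limit on interpretation, and the figure that would answer its question, power at 65 under the planning assumptions, appears nowhere in the SAP.

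**Working it through.** **Inputs.** Section 2.4: difference 1.8, SD 3.5 per group, 1-sided alpha 0.025 (critical value 1.960), allocations 124:61 and 43:22. Section 10.4: the conditional power formula. Assumption: all 65 randomised patients enter the mITT set, so n1=65, n=185 and n2=120. Differences are written so that positive favours TEV-50717.

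**Reproducing the SAP's figure.** SE = SD × √(1/n_T + 1/n_P) and power = Φ(difference/SE − 1.960).

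- 124:61: SE = 3.5 × √(1/124 + 1/61) = 0.547; 1.8/0.547 = 3.29; power = Φ(1.33) = 90.8% (noncentral t 90.5%). This agrees with the stated 90%.

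**The same calculation at the reduced sample.**

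- 43:22: SE = 3.5 × √(1/43 + 1/22) = 0.917; 1.8/0.917 = 1.96; power = Φ(0.00) = 50.1% (noncentral t 48.9%).
- If the SD were 3.0, power would fall from 97.0% to 62.9%. If it were 4.0, from 82.1% to 40.4%. These two SDs are an assumed range.

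**Item 1.** Section 10.4 gives CP = 1 − Φ[(z_α√n − z₁√n₁)/√n₂ − z₁√n₂/√n₁]. With n1=65 and n2=120:

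- z_α√(185/120) = 1.960 × 1.242 = 2.434
- √(65/120) + √(120/65) = 0.736 + 1.359 = 2.095
- so CP = Φ(2.095 z₁ − 2.434)

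The only free quantity is z₁, so CP maps one-to-one to the p-value.

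| 1-sided p | z₁ | CP for 185 |
|---|---|---|
| 0.30 | 0.52 | 9% |
| 0.20 | 0.84 | 25% |
| 0.123 | 1.16 | 50% |
| 0.10 | 1.28 | 60% |
| 0.059 | 1.56 | 80% |
| 0.05 | 1.645 | 84% |
| 0.025 | 1.96 | 95% |

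With no true effect, a non-significant result with CP of at least 50% would occur in 9.8% of trials, and with CP of at least 80% in 3.4%. If the true difference were 1.8 (SD 3.5), these would be 28.7% and 15.4%.

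**Item 2.** Neither Section 10.4 nor 10.5 gives a formula for this. The usual one is N = 65 × ((1.960 + 1.282)/z₁)², which gives 964 at p=0.20, 416 at p=0.10 and 252 at p=0.05. Solving CP = 0.90 for n instead gives 938, 388 and 222. Either way z₁ is the only outcome quantity that enters.

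**Item 3.** (1.960 + 1.282) × √(1/43 + 1/22) = 0.85 SD whatever the result, or 2.97 points at SD 3.5, against the planned 1.8. This does not depend on the observed effect.

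**What a near miss would show.** At z₁ = 1.56 and SD 3.5 the observed difference is 1.56 × 0.917 = 1.43. Its 95% CI is 1.43 ± 1.80, or −0.37 to 3.23. Item 1 would report 80%. Now keep the same accrued data but set the effect for the further 120 patients at the CI limits (z-scale 1.56 ± 1.96, that is −0.40 and 3.52):

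- lower limit: Φ(0.736 × 1.56 + 1.359 × (−0.40) − 2.434) = Φ(−1.83) = 3%
- upper limit: Φ(0.736 × 1.56 + 1.359 × 3.52 − 2.434) = Φ(3.50), above 99%

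The single figure of 80% conceals a range from 3% to over 99%.

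**The case against.** The strongest reply is that these are prespecified descriptive outputs attached to no success claim, threshold or decision. The primary test at 1-sided 0.025 (Sections 6.2.3 and 7) settles success, and Section 6.2.3 already plans the 95% CI. Section 2.5.1 says that little was known about treatment effects on this scale, so an interest in the observed effect is understandable, particularly for sizing a later study. All of this stands. It limits the consequence, but it does not make items 1 and 2 measure lost power.

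Three stronger readings might be inferred, and the SAP does not support them.

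- That the whole of Section 6.2.5 is unsound. Item 3 rests on the observed SD and the final sample size and bears directly on the reduction.
- That the section will make any failed trial look effective. The favourable figure arises only for a 1-sided p between 0.025 and about 0.12. At p=0.20 the same formula gives 25% and at p=0.30 it gives 9%, which would suggest that 185 patients would probably not have rescued the result.
- That the SAP claims the trial would have succeeded at 185. It makes no such statement. That is a foreseeable misreading of a near miss.

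Two technical reservations are fair. The n in Section 10.4 is an mITT count while 185 is a randomised count. With an assumed final mITT count of 58 to 65 and the total kept at 185, CP at p=0.10 runs only from 65% to 60%. The exact form of item 2 is inferred, since the SAP gives no formula for it.

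**Conclusion.** The point holds for items 1 and 2 only. For a given final sample size they are functions of the final z statistic and do not quantify what Section 6.2.5 says it will quantify. On the SAP's own planning values the loss is from about 91% to about 50% power, and the SAP does not state the second figure. For a non-significant result with a 1-sided p between 0.025 and about 0.12, item 1 would show 50% to 95% while the 95% CI includes zero.

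The risk is to interpretation. The primary test, type I error and the futility rule are unaffected. The figures rest on a normal approximation, the two-sample calculation that reproduces the SAP's 90%, arms of 43 and 22, and n1=65.

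**What to change.** - In Section 2.4, state the power at about 65 patients (43:22) under 1.8 and 3.5: about 50%, against about 91% at 124:61.
- In Section 6.2.5, report design-based power at the achieved sample size with the difference of 1.8 held fixed, once with SD 3.5 and once with the observed SD, beside the same calculation for 124:61.
- Keep item 3.
- Drop items 1 and 2. If they are kept, label them as descriptive, not a measure of lost power and not evidence of efficacy. Show them over the 95% CI limits of the effect as well as at the point estimate, and give the formula for item 2.
- Do not add an interpretive rule based on whether the CI excludes 1.8. At 43:22 and SD 3.5 the CI half-width is 1.96 × 0.917 = 1.80, so an upper limit below 1.8 would need an observed benefit of about zero or less. Moreover, 1.8 is a planning value diluted for missing data and not a relevance margin.

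The cost is a change of SAP wording, with no new data or analyses of substance. The downside for the sponsor is that a less favourable power figure, about 50%, is shown.
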